### 6.3 Part B (Multiple Dose)

Up to 30 participants will be sequentially assigned to one of three dosing groups (10 participants per group) starting with Group 1. Participants will be administered LMN-301 intranasally to each nostril at a fixed dose of 50 mg (25 mg in each nostril) every third day for 12 days (Group 1), every other day for 12 days (Group 2) or every day for 12 days (Group 3). All study participants will be observed in the clinic for 4 hours after the first dose.

Participants will be monitored for the occurrence of any adverse events (AEs) and serious adverse events (SAEs). Vital signs, physical exams and safety/laboratory testing will be performed on Days 1, 3 or 4, 7 and 14. Participants will use a diary (paper or electronic) to record any symptoms from the first dose through 28 days after the first dose.

Serum will be collected on Days 1 (baseline before dosing and 2 hours after dosing), 3 or 4, 7 and 14 for analysis to detect systemic absorption of virus-binding proteins and anti-drug antibodies (ADA).

Nasal mucosal lining fluid (MLF) samples will be collected using Synthetic Absorptive Matrix (SAM) strips (Nasosorption™ FX-I, Hunt Developments (UK) Ltd, United Kingdom) from all participants on Day 1 (baseline before dosing and 2 hours after dosing), and on Days

3 or 4, 7 and 14. Nasal MLF samples will be sent to Lumen Bioscience (Seattle, WA, USA) for analysis.

The schedule of assessments (SoA) for part B is presented in [Table 21-B](#) with a description of the study schedule and procedures provided in [Sections 10 and 11](#).

## 6.4 Safety Review

### 6.4.1 Safety Review Committee

There is no safety review committee for this study, however safety and tolerability data collected from the sentinel cohort participants will be reviewed by the principal investigator (PI), the independent medical monitor, and the sponsor medical monitor, either via email or meeting if required. The PI will decide whether to move forward with the multiple-dose cohorts (Part B) taking into account recommendations from the medical monitor and the sponsor medical monitor. The discussion will include review of the study and individual stopping rules.

### 6.4.2 Dose Stopping Rules

AEs which will prompt stopping the investigational product administration for all subjects and review include:

- Any individual experiencing any SAE considered at least possibly related to the investigational products; or
- If two or more subjects experience the same or similar unanticipated adverse event that is Grade 3 in severity or higher; or
- If the accumulation of SAEs and/or severe AEs collectively raises a safety concern in the opinion of the PI, Medical Monitor, or Sponsor.
- If any individual experiences liver function tests or creatinine increased to 3 times the upper limit of normal; or
- If any individual experiences significant spontaneous bleeding or platelet count  $< 100 \times 10^9/L$ ; or
- If any individual experiences coagulation disorders characterised by prolonged PT; or PTT or abnormal INR greater than 1.5 times the upper limit of normal
- If any individual experiences neutrophil values  $< 1.0 \times 10^9/L$

The decision to restart the study will be made by consensus of the Independent Medical Monitor, the sponsor's medical expert, and the Principal Investigator. The decision to stop the study will be communicated to the HREC and, similarly, the decision to re-start a study will also be communicated to the HREC.

Administration of the investigational product will be discontinued for any subject that develops:

- A serious adverse event considered at least possibly related to the investigational product; or
- An adverse event that is Grade 3 or higher and considered at least possibly related to the investigational product; or
- The Principal Investigator deems that stopping the investigational product administration is in the best interest of the subject.

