#### 4.2 Selection of Dose

The amount of powder to be administered is the maximum tolerated amount according to the device manufacturer Aptar.

The dose of LMN-301 selected for use in this clinical study (50 mg total per dose, delivered IN as 25 mg to each nostril) is comparable to the doses that were well tolerated in the hamster challenge studies. In the hamster study, 5 mg dry weight of extract was administered per nare, with each animal receiving 10 mg total dry weight. The estimated nasal surface area of a hamster is 1000 mm^2, compared with 18,000 mm^2 for humans, resulting in a scaling factor of 18x. A direct scaling of the well-tolerated hamster dose would therefore be 90 mg per nostril or 180 mg total per patient. This would significantly exceed the manufacturer's recommendation for the device. By administering less than 1/3 of the scaled equivalent dose already tested in hamsters, tolerability concerns are not expected.

Both therapeutic proteins in LMN-301 have low potential for systemic exposure and immunogenicity because of:

- their large size, which prevents intact systemic absorption
- the route of administration (intranasal)
- the lack of glycosylation and human Fc domains, which are required for active antibody transport mechanisms.

For further information, please refer to the Investigator Brochure.

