### 4.3 Risk/Benefit Assessment

The potential risks are those associated with phlebotomy and intranasal administration of LMN-301.

Anticipated reactions: Volunteers may experience localized reactions such as sneezing, nasal discharge, nasal tenderness or pain, or nasal irritation post intranasal administration of LMN-301.

Intranasally administered recombinant protein therapeutics have been evaluated in humans since the dawn of the modern biotechnology era. Starting in 1982 with recombinant interferon therapy (Scott et al., 1982), a wide range of therapeutic proteins have been safely tested in humans. As might be expected given what is known about the barrier function of mucosal tissues, across scores of independent clinical trials spanning four decades, none of these report significant adverse events plausibly related to the intranasally administered protein therapeutic (see, e.g., Scott et al., 1982; Higgins et al., 1983; Hayden et al., 1986; Heikkinen et al., 1998; Weltzin et al., 1999). Recent years have also seen an uptick in interest in probiotic therapies—including intranasally administered probiotics (Endam et al., 2021; Lambert et al., 2021; Marchisio et al., 2015; Mårtensson et al., 2017; Tran et al., 2022). Despite such investigational products being neither sterile (by definition) nor axenic, they confirm the intuitive result: mucosally delivered biologics are significantly safer than their injected counterparts.

These general lessons also extend to the particular details of LMN-301's formulation. Antibodies, VHVs, and other similar therapeutic proteins have been orally and intranasally administered in many human clinical trials without reports of SAEs or drug-related AEs (Carlton et al., 2018; Lochhead & Thorne, 2012; Nurbhai et al., 2019; Sarker et al., 2013). The safety, tolerability, and efficacy of intranasally administered therapeutic proteins against SARS-CoV-2 has been demonstrated in humans by at least six independent groups (de Vries et al., 2021; Haga et al., 2021; Huo et al., 2021; Imsuwansri et al., 2022; Nambulli et al., 2021; Song et al., 2023). Remarkably, three of these groups achieved these results using simpler, less potent versions of the VHH antibodies within LMN-301. All were safe and well-tolerated.

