## 6.6 Suspension or Termination of the Study at the Investigational Site

The Sponsor reserves the right to suspend or terminate an investigational site or this clinical study at any time. Reasons will be provided in the event of this happening. Reasons for termination may include, but are not limited to, the following:

- Unacceptable safety and tolerability;
- Serious or persistent noncompliance by the PI with the protocol, clinical research agreement, principles of the International Council for Harmonisation of Technical Requirements for Pharmaceuticals for Human Use (ICH) Good Clinical Practice (GCP), or applicable regulatory requirements in conducting the study;
- HREC decision to suspend or terminate approval for the PI;
- Regulatory authority request for study suspension or termination;
- Volunteer enrollment is unsatisfactory.

The PI reserves the right to withdraw from the study for safety reasons at any time following

---

consultation with the Sponsor.

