- Is considered unexpected (i.e., the event is not listed in the Investigator's Brochure or is not listed at the specificity or severity that has been observed). "Unexpected" as used in this definition, also refers to AEs that are mentioned in the Investigator's Brochure as occurring with a class of drugs or are anticipated from the pharmacological properties of the drug but are not specifically mentioned as occurring with the particular drug under investigation.

**Abnormal laboratory findings** (e.g., serum chemistry, haematology, coagulation, and urinalysis) **or other abnormal assessments** (e.g., vital signs, and physical examination

findings) that are judged by the PI as clinically significant (CS) will be recorded as AEs or SAEs if they meet the definitions stated above. Clinically significant abnormal laboratory findings or other abnormal assessments that are detected after the first administration of the study drug or are present at baseline and significantly worsen following administration of the study drug will be reported as AEs or SAEs. The PI will exercise his/her medical and scientific judgement in deciding whether an abnormal laboratory finding, or other abnormal assessment, is CS.

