**Table 12-A NCI-CTCAE 5-point Scale for Grading the Intensity of Each AE and SAE**

Grade		Definition
I	Mild	Asymptomatic or mild symptoms: clinical or diagnostic observations only; intervention not indicated.
II	Moderate	Minimal, local, or non-invasive intervention indicated; limiting age-appropriate instrumental ADL.
III	Severe	Severe or medically significant but not immediately life-threatening: hospitalisation or prolongation of hospitalisation indicated; disabling; limiting self-care ADL.
IV	Life-threatening	Life-threatening consequences: urgent intervention indicated.
V	Death	Death related to AE.

Abbreviations: ADL = activities of daily living; AE = adverse event.

If an AE/SAE has multiple aspects (symptoms), the aspect with the highest severity will be graded.

The term severe is a measure of severity. Thus, a severe AE is not necessarily serious. For example, itching for several days may be rated as severe, but may not be clinically serious.

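### Two related, non-serious Grade 3 nasal reactions need not trigger a study-wide pause, because the two-subject stop counts only events that are unanticipated, a term the protocol leaves undefined

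*Protocol*

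**What the plan says.** Protocol 6.4.2 lists the events that stop dosing for all participants and prompt a review. Its second bullet applies "If two or more subjects experience the same or similar unanticipated adverse event that is Grade 3 in severity or higher". Section 6.4.2 does not say what makes an event unanticipated, and no other section defines the word.

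Section 4.3 states: "Anticipated reactions: Volunteers may experience localized reactions such as sneezing, nasal discharge, nasal tenderness or pain, or nasal irritation post intranasal administration of LMN-301". It gives no severity limit.

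The other study-wide triggers in 6.4.2 are:
- one SAE that is at least possibly related;
- an accumulation trigger, "If the accumulation of SAEs and/or severe AEs collectively raises a safety concern in the opinion of the PI, Medical Monitor, or Sponsor";
- laboratory and bleeding criteria for liver function, creatinine, platelets, coagulation and neutrophils.

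A separate rule in 6.4.2 stops dosing in the individual for "An adverse event that is Grade 3 or higher and considered at least possibly related to the investigational product". That rule does not ask whether the event was anticipated. Section 6.6 adds a general power: "The Sponsor reserves the right to suspend or terminate an investigational site or this clinical study at any time".

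On review, sections 6.4.1 and 10.3 plan one look at the safety data, after the sentinel cohort and before Part B. The Synopsis (Safety Review) provides for a review within Part B if stopping criteria are met. Section 6.3 fills the Part B groups in sequence, beginning with Group 1, and Table 8-A sets 4, 6 and 12 doses for Groups 1, 2 and 3.

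**The concern.** Safety and tolerability is the primary objective, and the solicited events are local nose and throat symptoms plus cough. The local reactions in 4.3 are the toxicity the protocol itself expects from this powder. Yet the only numeric study-wide stop based on clinical severity excludes anticipated events, and 4.3 places those reactions under that label at any grade.

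Within Part B, a review follows only if a stopping criterion is met, so the wording of this bullet has practical weight. Suppose two people in Group 1 have severe, related nasal pain. Whether the data must be reviewed before others start every-other-day and then daily dosing depends on how one undefined word is read, or on someone choosing to halt.

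**Working it through.** **Step 1. Test the scenario against each rule.** The scenario is two participants with the same related, non-serious Grade 3 reaction named in 4.3. It can occur under the protocol's own grading, because the text below Table 12-A says "Thus, a severe AE is not necessarily serious".

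| Rule | Met? | Mandatory for all? |
|---|---|---|
| Related SAE (6.4.2) | No, not serious | – |
| Two-subject Grade 3 (6.4.2) | No, if read as anticipated under 4.3; yes, if severity makes it unanticipated | Only on the second reading |
| Accumulation (6.4.2) | Only if the PI, Medical Monitor or Sponsor has a safety concern | No, depends on opinion |
| Laboratory and bleeding (6.4.2) | No; the four named reactions are neither | – |
| Individual discontinuation (6.4.2) | Yes, for both | No, those two only |
| Sponsor suspension (6.6) | At the sponsor's choice | No |

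If 4.3 settles what is anticipated, no mandatory study-wide trigger is met.

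**Step 2. Exposure that could follow.** The inputs are the doses and group sizes in Table 8-A. The assumption is that nobody uses the discretionary powers.
- Both cases in Group 1, later groups dosed in full: 10 × 6 + 10 × 12 = 180 doses in 20 participants.
- Both cases on Day 1 of Group 1, with all ten starting together (the protocol does not say they do): the other eight have three doses left, 8 × 3 = 24, so 180 + 24 = 204.

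**Step 3. How often the added trigger would fire.** As a check on the binomial method, the plan's sample-size statement (Protocol 13.1, SAP 3) reproduces: 1 − 0.9^35 = 97.5% (stated as over 97%) and 1 − 0.9^30 = 95.8% (stated as over 95%).

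The documents give no Grade 3 rate, so the rate p of a related Grade 3 event for one reaction is an assumption. The chance of at least two cases is P = 1 − (1−p)^n − n·p·(1−p)^(n−1).

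| Assumed p | One group, n=10 | Part B, n=30 | All, n=35 |
|---|---|---|---|
| 0.5% | 0.1% | 1.0% | 1.3% |
| 1% | 0.4% | 3.6% | 4.8% |
| 2% | 1.6% | 12.1% | 15.5% |
| 5% | 8.6% | 44.6% | 52.8% |
| 10% | 26.4% | 81.6% | 87.8% |

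Section 4.3 names four reactions. If each has rate p independently, then in Part B (n=30) at p = 0.5%, 1% and 2%:
- counted separately, 1 − (1−P)^4 = 3.9%, 13.7%, 40.2%;
- pooled as similar, with q = 1 − (1−p)^4 = 1.99%, 3.94%, 7.76%, the chance of two or more is 11.9%, 33.2%, 68.8%.

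If the four always occur in the same people, these fall back to the one-reaction figures. The calculation stops at four because solicited events that 4.3 does not name, such as loss of smell or cough, may already count as unanticipated. A pause for those would not be an added cost.

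**The case against.** The strongest reply is that 6.4.2 already deals with this. The accumulation bullet is itself a study-wide stop, names severe events, does not ask whether they were anticipated, and needs a concern from only one of three parties. Restart then requires consensus. One related SAE stops everyone, each affected participant stops, and the trigger list is introduced as inclusive. All of this stands. It shows that a pause is permitted, but not that one is required.

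The second reply is that Grade 3 severity makes a nasal reaction unanticipated. Table 12-A describes Grade III as severe or disabling, section 4.2 says "tolerability concerns are not expected", and the SUSAR definition in 12.1 treats an event as unexpected if it "is not listed at the specificity or severity that has been observed". This reading is plausible. However, the 12.1 text defines a different word, serves SUSAR classification, refers to the Investigator's Brochure (not among the documents here), and is not linked to 6.4.2. Two careful readers could reach opposite answers.

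Third, the individual and study-wide rules have different purposes, so a difference between them is not a contradiction. That is right: a reader might infer that 6.4.2 conflicts with itself, and it does not. The difference shows only that the same event can be serious enough to stop one person without compelling a look at the others.

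Fourth, no Grade 3 rate anchors the probabilities. That also stands. They describe the cost of the fix across a range and do not predict what will happen.

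**Conclusion.** The point holds in a narrow form. If the reactions in 4.3 count as anticipated at every grade, two related, non-serious Grade 3 nasal reactions meet no mandatory study-wide trigger, and a pause and review become a matter of judgement.

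A reader might go further and infer that the protocol has no means of stopping for severe nasal reactions, or that Part B would continue without review. The documents do not support that: three parties can each invoke the accumulation bullet, the sponsor can suspend, and any related SAE stops dosing for all. Nor are 180 or 204 doses a forecast. They are upper limits that require every party to decline to act, and 204 also requires simultaneous Day 1 dosing.

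Priority is minor to moderate. The gap is small, but it lies at the main expected local toxicity, in a design where dosing frequency rises by group with no scheduled review between groups, and it is cheap to close.

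**What to change.** Replace the second bullet of 6.4.2 with: *two or more participants have the same or a similar adverse event of Grade 3 or higher that is either (a) unanticipated, or (b) a local nasal or throat reaction judged at least possibly related to LMN-301, whether or not anticipated.*

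Leave 4.3, the accumulation bullet, the individual rule and the consensus restart as they are. Limb (a) keeps the undefined word, but the word no longer decides what happens to related local reactions. Adding a grade limit to 4.3 instead would be less precise: unrelated Grade 3 nasal symptoms, for example from a cold, would then enter through limb (a), which does not require relatedness.

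The change is one bullet by protocol amendment, with no extra visits, samples or participants. The downside is more temporary pauses, with the chances shown in the working. The high pooled figure of 68.8% arises when 7.76% of healthy volunteers, who can expect no treatment benefit, have a related Grade 3 local reaction. A compulsory review is reasonable in that case.

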## 6.5 Participant Withdrawal Criteria

Participants will be advised that they are free to withdraw from the study at any time for any reason or, if necessary, the PI (or delegate) may discontinue a participant from the study to protect the participant's health. A participant may voluntarily withdraw or be withdrawn from the study for reasons including, but not limited to, the following:

- The need to take medication which may interfere with study measurements.
- Intolerable/unacceptable AEs.
- Positive test for Covid-19
- Noncompliance of the participant with the protocol.
- Withdrawal of consent; or
- If, in the PI's (or delegate's) judgement, it is in the participant's best interest.

The Sponsor will be notified as soon as possible of any participant withdrawals. The date and reasons for withdrawal will be recorded in the eCRF and included in the final clinical study report, along with any AEs and necessary medical treatment (up until the point of study withdrawal).

Any participant who prematurely discontinues study drug, should have, if possible, all scheduled safety assessments performed, including all follow-up visit assessments as scheduled. If a participant withdraws from the study, an attempt should be made to collect all remaining safety samples scheduled for that day.

In the event that a participant is discontinued from the study due to an SAE, the PI (or delegate), or medically trained nominee, will evaluate the urgency of the event. If the situation warrants, the PI (or delegate), or medically trained nominee, will take appropriate diagnostic and therapeutic measures and attempt to notify the sponsor's medical expert. If the situation is not an immediate emergency, the PI (or delegate), or medically trained nominee, at the clinical facility will attempt to contact the sponsor's medical expert for consultation. No medical help, diagnosis, or advice will be withheld from the participant due to an inability to contact the sponsor's medical expert. The participant will be encouraged to remain available for follow-up medical monitoring.

Participants who withdraw from the study prior to treatment will be replaced according to recruitment and enrolment processes outlined in [Section 7.3](#).

## 6.6 Suspension or Termination of the Study at the Investigational Site

The Sponsor reserves the right to suspend or terminate an investigational site or this clinical study at any time. Reasons will be provided in the event of this happening. Reasons for termination may include, but are not limited to, the following:

- Unacceptable safety and tolerability;
- Serious or persistent noncompliance by the PI with the protocol, clinical research agreement, principles of the International Council for Harmonisation of Technical Requirements for Pharmaceuticals for Human Use (ICH) Good Clinical Practice (GCP), or applicable regulatory requirements in conducting the study;
- HREC decision to suspend or terminate approval for the PI;
- Regulatory authority request for study suspension or termination;
- Volunteer enrollment is unsatisfactory.

The PI reserves the right to withdraw from the study for safety reasons at any time following

---

consultation with the Sponsor.

## 6.7 Treatment Allocation

All study participants who sign an informed consent form at screening will receive a unique sequential number (i.e., a screening number). Participants will be allocated to the next available treatment group in the order they are screened. As this is an open-label study, no randomisation or blinding will occur.

# 7 PARTICIPANT SELECTION

The screening period starts with the signing of the informed consent. During the screening period, inclusion/exclusion criteria for the study participation will be checked/tested. Subjects who meet all inclusion criteria and do not meet any exclusion criterion will be eligible to be enrolled. Those who are not eligible for enrollment or dosing will be considered as screening failures. Data for screen failure reason, eligibility criteria, and demography will be captured on the appropriate screening and enrolment log.

Assessments may be repeated once, if abnormal values were recorded in the first instance, at the discretion of the PI. Values outside of the ranges specified in the criteria below may be considered acceptable if determined by the Investigator (in conjunction with the study medical monitor) to be not clinically significant (NCS).

Unless specifically defined below, inclusion and exclusion criteria are to be assessed at screening and again on Day 1, prior to dose administration.

